4.3 Inclusion Criteria

- Males and females, 18 to 65 years of age
- BMI 18 to <35.0 kg/m², inclusive
- Weight is ≥ 110 lbs
- Subject is judged to be in good health on the basis of medical history
- Subject is willing to fast overnight, prior to study start
- Subject is willing to avoid alcohol and intense physical activity the day prior to and on the day of testing
- Subject is capable of giving informed consent and complying with all study procedures/ requirements.

4.4 Exclusion Criteria

- Previous GI disorders (e.g., inflammatory bowel disease, irritable bowel syndrome, history of surgery for weight loss, or gastroparesis)
- Gastroenteritis in the 2 weeks preceding the study
- Weight <110 lbs
- Diabetes
- History of alcohol or drug abuse
- Previous diagnosis of neurological disorders, depression, or mental illness with psychosis
- Unexplained alarm features (i.e., unintentional weight loss >10% body weight in the last 3 months, fevers, or blood in stools)
- Use of an antibiotic or any medication impacting gut transit during the 2 weeks before the study
- Constipation or diarrhea (defined as, on average, less than 3 stools per week or more than 3 stools per day, respectively)
- Allergy to tree nuts
- Women who are pregnant or breastfeeding;
- Persons with medical conditions affecting the pancreas, liver, thyroid, or gall bladder.

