3.1 General Design

The clinical trial described herein is an open-label, acute study involving a total of 30 healthy male and female adults (ages 18 to 65 years; BMI of 18 to <35.0 kg/m², inclusive).

Prior to the clinical study, subjects will be screened according to the study inclusion and exclusion criteria, using an online survey (**Appendix A**). Subjects meeting all the inclusion criteria and none of the exclusion criteria will be invited to participate in the study (Table 3.1-1). These subjects will be sent study equipment and materials, including 1 consent form. Subjects will be asked to read the consent form and e-mail either the Research Associate or the Principal Investigator with any specific questions. If there are no questions, or once the questions have been resolved, those that wish to participate will be asked to sign the consent form and send a picture of the signed page to the Research Associate of the study.

Therefore, the subject will maintain a copy of the signed consent form, as per the U.S. Food and Drug Administration's regulations.

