On the day of the clinical study, subjects will follow instructions for study methodology (**Appendix B**). Subjects, who will have fasted overnight for 12 hours, will self-assess and record GI symptomology [using the modified visual analogue scale (mVAS) GI symptoms tool], alertness [using the Stanford Sleepiness Scale (SSS)], and blood BHB level (using the Keto Mojo BHB monitor), at time 0 minutes, as baseline measures, using an online study portal (**Appendix C**). Subjects will then consume 3 servings of Avela™, each providing 11.5 g of (R)-1,3-butanediol, with the first serving consumed at 0 minutes, the second serving at 30 minutes, and the third serving at 60 minutes. After the collection of baseline measures (at 0 minutes), GI symptomology (assessed using the mVAS GI symptoms tool), alertness (assessed using the SSS), and blood BHB levels (using the Keto Mojo BHB monitor) will be assessed, again, at 30, 60, 90, 120, 180, 240, and 300 minutes. At each time point, it is important that the order of collection be maintained [*i.e.*, 1. GI symptomology; 2. Alertness/sleepiness; 3. BHB level; and 4. Avela™ (when Avela™ is to be consumed; *i.e.*, at 0, 30, and 60 minutes)]. After the assessments at 240 minutes are complete, subjects will consume 1 ALOHA Organic Plant Based Protein Bar (Caramel Sea Salt). During the study, subjects will be asked to record their blood BHB levels and questionnaire results using the online portal (**Appendix C**). The results will be recorded electronically, using a de-identified survey on Survey Monkey, designed to protect subject anonymity [*i.e.*, the survey will not be affiliated with a name or any personal information; rather, each participant will have a unique identification number, which will be used to access the survey and upload the results of the study).

Number of Subjects	Investigational Product; Dose
30 subjects (males and females)	(R)-1,3-butanediol; 3 doses of 11.5 g/dose

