4.2 Total Number of Subjects and Sites

The proposed clinical study is being conducted by Genomatica. Thirty Genomatica employees (males and females) are being recruited for the study. There is no sample size calculation, as there is no control group and the study is a pilot study, with the main objective of understanding ketone (BHB) levels following consumption of (R)-1,3-butanediol. 30 participants are to be included, due to the inherent

variability in the GI symptomology questionnaires. Of note, in other studies of food ingredients (e.g., inulin¹, sorbitol², erythritol + fructose³) where GI tolerance was an outcome of interest, sample sizes ranged from 26 to 37 participants

Genomatica employees who express interest in participating in the study and who meet the eligibility criteria for study inclusion will complete the study remotely, within their own homes, using equipment provided by Genomatica (i.e., lancets, sharps container, alcohol swabs, Keto Mojo BHB monitor and ketone test strips (and glucose test strips, not to be used in the study), bandages, pregnancy test [if applicable], measuring tape, three 4 oz. (118 mL) bottles of sealed water premixed with Avela™ [each providing 11.5 g of (*R*)-1,3-butanediol], 1 shot glass with the Avela™ logo, an ALOHA Organic Plant Based Protein Bar (Caramel Sea Salt), 1 duffel bag, 1 consent form, and study instructions. All study-related data will be entered and transmitted by each study participant using an electronic platform, using surveys that will protect the identity of each participant.

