5.3 Subject Compliance Monitoring

Compliance of subjects will be assessed by using compliance records. Participants must consume all 3 doses of product, at the specified timepoints, to meet compliance requirements.

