- Using the online portal, the subject will:
 - Complete the mVAS GI symptoms tool.
 - Complete the SSS.
- Measure their blood BHB level using the Keto Mojo Monitor and record the value on the online portal.

6.2.7 180 min timepoint

- Using the online portal, the subject will:
 - Complete the mVAS GI symptoms tool.
 - Complete the SSS.
- Measure their blood BHB level using the Keto Mojo Monitor and record the value on the online portal.

6.2.8 240 min timepoint

- Using the online portal, the subject will:
 - Complete the mVAS GI symptoms tool.
 - Complete the SSS.
- Measure their blood BHB level using the Keto Mojo Monitor and record the value on the online portal.
- Consume the provided ALOHA Bar within 7 minutes.

6.2.9 300 min timepoint

- Using the online portal, the subject will:

- Complete the mVAS GI symptoms tool.
- Complete the SSS.
- Measure their blood BHB level using the Keto Mojo Monitor and record the value on the online portal.

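### Tree-nut allergy is the only allergy exclusion, yet every participant is told to eat a commercial protein bar at home, and no criterion expressly screens for allergy or intolerance to its other ingredients

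*Combined protocol and SAP*

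**What the plan says.** Section 4.4 lists twelve exclusions. The only one that concerns allergy is "Allergy to tree nuts", and the synopsis carries the same item. Section 3.1 makes the listed criteria decisive, applied through an online survey: "Subjects meeting all the inclusion criteria and none of the exclusion criteria will be invited to participate in the study".

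Two inclusion criteria in section 4.3 bear indirectly on the point. One is general health: "Subject is judged to be in good health on the basis of medical history". The other asks that the subject can give consent and comply with the study procedures.

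The bar is part of the kit listed in sections 4.2 and 5.5.1. Table 5.1-1 and Table 6-1 schedule it for everyone at 240 minutes, after that timepoint's assessments. The instruction in section 6.2.8 is "Consume the provided ALOHA Bar within 7 minutes". Appendix B repeats it, also without a condition. Section 4.2 has the study done remotely in participants' homes, and section 7.1 plans no clinical evaluations.

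The drink is described in section 4.2 as "three 4 oz. (118 mL) bottles of sealed water premixed with Avela™", and section 1.3 gives the product's purity as at least 99.7%.

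**The concern.** The protocol accepts that a food allergy can decide eligibility, but it names one allergen. The drink is described as water plus a highly purified single compound, so the tree-nut item is most plausibly there because of the bar. That is an inference; the protocol gives no reason for the item. If the bar's contents matter for eligibility, the criterion should cover all of them.

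Two things are at stake. The first is participant safety: the bar is not the product under study, so a reaction to it is a risk that answers no study question, and it would occur where no staff presence is described. The second is interpretation. Unsolicited adverse events are the primary safety endpoint (section 3.3) and GI symptoms are a secondary endpoint (section 3.2.2). With one group and no control (sections 4.2 and 5.2), a reaction to the bar late in the session could be hard to tell apart from an effect of the study product.

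**Working it through.** The plan states no figure to reproduce on this point, and N = 30 is not affected. The check is a comparison of the text, followed by a simple count.

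**1. Who is screened out for allergy?**
- Section 4.4: 12 items. One concerns allergy (tree nuts). None concerns another food allergy, a food intolerance, or hypersensitivity to the study product.
- Synopsis: the same count.
- Section 4.3: neither the good-health criterion nor the able-to-comply criterion mentions allergy.

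**2. Who eats the bar?** All participants, so 30 of 30, at home at 240 minutes (sections 3.1, 4.2 and 6.2.8; Tables 5.1-1 and 6-1; Appendix B). No exception for allergy is written in any of these places.

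**3. What is known about the bar's contents?** Only its trade description as a plant-based protein bar with a caramel and sea-salt flavour. It presumably contains a plant protein and flavouring, but no ingredient list is given.

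**4. Which data could a reaction to the bar reach?** Assessments are at 0, 30, 60, 90, 120, 180, 240 and 300 minutes: 8 timepoints. The bar follows the 240-minute assessments, so only the 300-minute readings come after it: 1 of 8. Adverse event reporting continues to the evening of the test day (section 9.1), so later reports could also be affected. Symptoms that began before the bar was eaten could not be due to it.

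**5. What would one such event be worth?** With 30 participants, 1/30 = 0.033, or 3.3 percentage points of an adverse event rate. Section 8 specifies no test or threshold for that rate, so the shift is descriptive only.

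**The case against.** The strongest case against has five parts.

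- **Other criteria may do the work.** A person who knows they cannot eat the bar arguably cannot comply with a scheduled procedure, and so fails section 4.3. The GI-disorder exclusion, whose examples are not exhaustive, may catch some intolerances. This stands in part. A reader might infer that an allergic person satisfies all the criteria, and that goes too far. But none of these criteria asks about allergy, and a person with a food allergy can be in good health.
- **The participant can decline.** An adult with a known allergy may simply not eat a named commercial bar. Section 5.3 ties compliance to the study product rather than the bar: "Participants must consume all 3 doses of product, at the specified timepoints, to meet compliance requirements". However, section 4.6.1 counts failure to meet other study obligations as poor compliance, so the protocol does not clearly offer refusal as an option.
- **The missing material may answer the point.** The screen captures in Appendices A and C and the consent form are not in the copy reviewed, and they may ask about or list allergens. This stands as a limit. Section 3.1 says the survey applies the listed criteria, so the criterion itself should still be complete.
- **Tree nuts may be the only relevant allergen in the bar.** The documents cannot settle this either way.
- **The drink is not a comparable exposure.** This stands. A reader might extend the point to a multi-ingredient drink, but the documents describe only water and the study product. What is absent there is an exclusion for known allergy or intolerance to the product itself.

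**Conclusion.** The point holds as a minor eligibility gap. The written rule covers one allergen, all 30 participants are told to eat the bar, and nothing in the criteria expressly screens for allergy or intolerance to its other ingredients. It rests on the assumption that the bar has at least one other ingredient to which someone could react, which its name suggests but no ingredient list confirms.

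The effect on the data is confined to the 300-minute readings and later adverse event reports, at 3.3 percentage points of an adverse event rate per event.

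Three stronger readings are tempting and are not supported:

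- **Unaccompanied participants.** The text says remotely and at home. It describes no staff presence, but it does not say that nobody else is there.
- **Certain misattribution to the product.** Section 4.6.1 has relatedness grades that include none and remote, and section 9.3 provides for an assessment of association as needed. Such an event could be hard to separate from a product effect; it need not be blamed on the product.
- **A quantified chance of trouble.** The documents give no prevalence of allergy or intolerance to the bar. Any probability built on an assumed one would count people who could be enrolled, not reactions.

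**What to change.** In section 4.4 and the synopsis, replace the tree-nut item with: *Known allergy or intolerance to tree nuts, to any other ingredient of the ALOHA bar, or to the study product.* Align the corresponding question in the Appendix A screening survey, and show the bar's ingredient list beside it if the survey does not already do so.

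The cost is one reworded criterion in two places and one survey item. The downside is possibly one or two fewer eligible volunteers. Sample size, endpoints, study product and schedule are unchanged.

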4.5 Subject Recruitment

All subjects will be employees of Genomatica Inc., located in San Diego, California. Participation in the study is not a requirement of employment, and measures are being taken to ensure that Genomatica employees do not feel coerced to partake in the study. An employee's decision about research participation will not affect (favorably or unfavorably) performance evaluations, career advancement, or other employment-related decisions made by peers or supervisors.

¹ Example study (Bonnema *et al.*, 2010) available at: <https://doi.org/10.1016/j.jada.2010.03.025>

² Example study (Fernández-Bañares *et al.*, 2005) available at: <https://pubmed.ncbi.nlm.nih.gov/16410032/>

³ Example study (Kim *et al.*, 2011) available at: <https://pubmed.ncbi.nlm.nih.gov/22118754/>

4.6 Early Withdrawal of Subjects

4.6.1 When and How to Withdraw Subjects

Subjects may withdraw consent or be removed from the study by the Principal Investigator (PI). In the event that a subject is withdrawn from the study, the reason for the withdrawal will be documented, with the primary reason selected from the following standard categories:

- Withdrawal of consent: the subject requests to withdraw from further participation in the study in the absence of a medical need to withdraw as determined by the PI.
- Lost to follow-up: for unknown reasons, the subject did not upload their study results on to the electronic platform.
- Poor compliance: the subject consumes only 1 or 2 of the 3 servings of the study product; is found to meet an exclusionary criterion; and/or is not complying with other study obligations.
- AE: in the judgment of the PI and in the best interests of the subject, events that require discontinuation of study product (includes all categories of study product relatedness: None, Remote, Possible, Probable, or Highly Probable).
- Death: death of the subject.
- Other: causes of premature termination from the study other than the above, such as theft or loss of study products, termination of study by Sponsor, *etc.*

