1.6 Dose Rationale and Risk/Benefits

The study dose was chosen based on the level of (R)-1,3-butanediol that was determined to be GRAS for use. Thus, during the test day, study participants will consume 3 servings of Avela™; each serving will provide 11.5 g of (R)-1,3-butanediol. Effects on ketone (BHB) production, GI tolerance, and sleepiness/alertness will be assessed.

2 Study Objectives

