4.6.2 Data Collection and Follow-up for Withdrawn Subjects

Should a subject request to withdraw or be withdrawn from the study by the PI, the subject's reason for withdrawal will be documented.

5 Study Product

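### A participant who declines a serving because of symptoms may be withdrawn for poor compliance, and no further GI tolerance forms are then required

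*Combined protocol and SAP*

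**What the plan says.** GI tolerance is a secondary objective (Section 2.2), and Section 1.6 states that "Effects on ketone (BHB) production, GI tolerance, and sleepiness/alertness will be assessed". Section 4.2 gives the variability of the GI questionnaires as the reason for including 30 participants.

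Section 4.6.1 says that subjects may be removed by the PI, and that one primary reason is chosen from a list. Two entries matter most here:

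- "Poor compliance: the subject consumes only 1 or 2 of the 3 servings of the study product". This bullet makes no exception for symptoms.
- AE, defined as "in the judgment of the PI and in the best interests of the subject, events that require discontinuation of study product", at any level of relatedness.

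Section 5.3 adds: "Participants must consume all 3 doses of product, at the specified timepoints, to meet compliance requirements".

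The section on data from withdrawn subjects, 4.6.2, consists of one sentence: "Should a subject request to withdraw or be withdrawn from the study by the PI, the subject's reason for withdrawal will be documented".

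Servings are taken at home at 0, 30 and 60 minutes. The mVAS is completed at 0, 30, 60, 90, 120, 180, 240 and 300 minutes, each time before any serving due then. Section 3.1 stresses the sequence: "At each time point, it is important that the order of collection be maintained". Appendix B has no step for a participant who does not want the next serving.

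**The concern.** Refusing the next serving because of nausea or taste is itself evidence about tolerance. The poor-compliance bullet fits such a refusal on its wording and names no symptom. The AE category fits too, but only if the PI judges that the event required stopping. A participant alone at home with 30 minutes between servings may well decide before the PI is consulted. Nothing says which category prevails when both apply.

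The coding is the smaller matter. Both categories are reasons for leaving the study, and once a participant has left, Section 4.6.2 asks for nothing but the reason. If the PI applies the rule, GI scores stop early in the people most likely to have symptoms, and the later mVAS summaries describe those who took all three servings. On a single test day, forms that were not completed cannot be recovered afterwards.

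**Working it through.** The plan states no figure on this point. Section 4.2 says that there is no sample size calculation, and no stopping or dropout rate appears anywhere. The check therefore reads the codes side by side and counts forms from the schedule.

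**1. Codes applied to one case.** A participant takes servings 1 and 2, scores nausea 6 on the mVAS at 60 minutes, and declines serving 3.

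- Poor compliance: met, since 2 of 3 servings were taken.
- AE: met if the PI judges that the event required stopping.
- Withdrawal of consent: limited to withdrawal "in the absence of a medical need to withdraw as determined by the PI", so it fits poorly.
- Lost to follow-up: "Lost to follow-up: for unknown reasons, the subject did not upload their study results on to the electronic platform". It does not fit when the reason is known.

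The real ambiguity is between poor compliance and AE.

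**2. Forms not required after withdrawal.** Inputs: the mVAS times and serving times in Table 5.1-1 and the order of events in Table 6-1. The post-dose forms are at 30, 60, 90, 120, 180, 240 and 300 minutes, which makes 7.

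| Withdrawn on declining | Post-dose forms completed | Forms not required | mVAS follow-up after last serving |
|---|---|---|---|
| Serving 2, at 30 min | 30 | 60, 90, 120, 180, 240, 300 = 6 of 7 | 30 − 0 = 30 min |
| Serving 3, at 60 min | 30, 60 | 90, 120, 180, 240, 300 = 5 of 7 | 60 − 30 = 30 min |
| None (completer) | all 7 | 0 of 7 | 300 − 60 = 240 min |

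**3. What this could do to a result (illustration only).** Assumptions, none of them in the documents: 2 completers score 5 or more (severe in Section 7.3.1) after 60 minutes; *k* others stop, are withdrawn and complete no further forms; each of them would also have scored 5 or more after 60 minutes.

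Observed share after 60 minutes = 2/(30 − *k*). Share in all 30 = (2 + *k*)/30.

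| *k* | Observed | All 30 | Difference |
|---|---|---|---|
| 0 | 2/30 = 6.7% | 2/30 = 6.7% | 0 |
| 1 | 2/29 = 6.9% | 3/30 = 10.0% | 3.1 points |
| 3 | 2/27 = 7.4% | 5/30 = 16.7% | 9.3 points |
| 5 | 2/25 = 8.0% | 7/30 = 23.3% | 15.3 points |

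**4. The same case with another summary.** Suppose the stoppers had already scored 5 or more on the form completed just before they declined, and the summary is any severe score at any post-dose time, with everyone who took a serving included. The observed share is then (2 + *k*)/30, equal to the share in all 30, and the understatement is 0 for every *k*. The size of the effect thus depends on the summary chosen as well as on *k*, and the plan fixes neither.

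**The case against.** The case on the other side is substantial, and most of it stands.

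- The AE category is in the same list and can take symptom-driven stops. A reader might infer that the protocol has no route for them. It has one, although that route depends on PI judgment and has no stated priority.
- Removal is discretionary. A reader might infer that a missed serving ends participation automatically and that the later forms are never collected. The text does not say so. Section 7.3.1 expects the mVAS from every subject through 300 minutes, the Appendix B steps from 90 minutes on do not depend on servings taken, and no same-hour removal procedure is described. Someone who skips a serving could simply carry on with the forms.
- A reader might infer that withdrawn participants are left out of the analysis. Section 8 defines no analysis set, so the documents neither say this nor rule it out.
- Symptoms leading to the refusal are already scored, and Section 5.5.2 requires a record of doses consumed. With 30 participants, stoppers could often be identified from these records and the documented reason.
- Section 9 keeps AE recording open to the evening of the test day and requires unresolved AEs to be followed. This does not replace graded scores at fixed times. The space for other AEs also sits at the end of the mVAS (Section 9.1), so that route closes if the forms stop.
- Prior experience is mixed. Four of the nine cyclists in one cited study retched because of taste, though the protocol does not say that any failed to finish. The cited running study, with three divided doses, reported no adverse GI effects. Neither gives a stopping rate for this product and setting.
- The portal screens and consent form were not available for this review and may already deal with a declined serving.

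What remains is that the poor-compliance rule, where applied, makes stopping the product a ground for leaving the study, and that the section governing withdrawn subjects asks for no further assessments.

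**Conclusion.** The point holds as a risk of informative dropout from a secondary endpoint. Poor compliance has no symptom exception and is not ranked against AE, and under either code a withdrawn participant is not asked for the remaining 5 or 6 of 7 post-dose mVAS forms. Those counts follow from the schedule, given that the PI withdraws the participant at the refusal and no later forms are entered.

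The size of any bias is unknown. The 3.1 to 15.3 point differences should not be read as an estimate: they need an assumed number of stoppers, an assumed later severe score in every one of them, and a summary confined to the period after 60 minutes. With no stoppers, or with the any-time summary in step 4, the difference is zero. The change is worth making because it is cheap and missed forms cannot be recovered, not because a bias has been shown.

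**What to change.** - **Section 4.6.1:** state that declining a serving is not in itself withdrawal from the study. Record a stop because of symptoms or taste as such (AE or intolerance), including when it is the participant's own decision, and give that reason precedence over poor compliance. Section 5.3 needs only a matching cross-reference.
- **Section 4.6.2:** invite anyone who declines a serving to complete the remaining mVAS and SSS forms to 300 minutes, voluntarily. Fingersticks can be optional.
- **Appendix B, at 30 and 60 minutes:** add a line such as: If you do not want this serving, do not drink it; record why, and continue the questionnaires if you are willing.
- **Reporting:** give GI tolerance for everyone who took at least one serving, with servings taken shown beside it and the number who stopped for symptoms or taste reported as a tolerability result. The BHB curve may be limited to those who took all three servings.

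The cost is a few sentences, two instruction lines and perhaps one portal item, with no extra visits or product. There are two downsides. Someone who feels unwell is invited to complete forms at 5 or 6 further timepoints, so continuing must be truly voluntary, particularly because participants are employees of the sponsor. The GI summary will also mix one-, two- and three-serving exposures, which is why servings taken must be shown.
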